3.2 Exclusion Criteria

3.2.1. Women who are pregnant or lactating.

3.2.2. Patients with evidence of non-hepatic metastatic disease.

3.2.3. Local conditions or systemic illnesses which would reduce the local tolerance to radiation treatment, such as serious local injuries, active collagen vascular disease, etc.

3.2.4 Prior liver directed radiation treatment.

3.2.5 Patients may have no serious medical illness, which may limit survival to less than 3 months.

3.2.6 Patient may have no serious psychiatric illness/social situations which would limit compliance with study requirements.

CONFIDENTIAL

This document is confidential. Do not disclose or use except as authorized.

- 3.2.7** Patients who have had chemotherapy (other than 5-fluorouracil, capecitabine, or sorafenib) or radiotherapy within 4 weeks (6 weeks for nitrosoureas or mitomycin C) prior to entering the study or those who have not recovered from adverse events (with the exception of anticipated chronic late effects from chemotherapy not expected to be exacerbated by radiation) due to agents administered within the timeframes described in 3.1.3 above.
- 3.2.8** Patients may not be receiving any other study agents.
- 3.2.9** Uncontrolled intercurrent illness including, but not limited to ongoing or active infection, symptomatic congestive heart failure, unstable angina pectoris, cardiac arrhythmia,
- 3.2.10** Individuals with a history of a different malignancy are ineligible except for the following circumstances; They have been disease-free for at least 5 years and are deemed by the investigator to be at low risk for recurrence of that malignancy.
- 3.2.11** Because no dosing or adverse event data are currently available on the use of high dose liver radiation participants <18 years of age are excluded from this study.

3.3 Inclusion of Women, Minorities and Other Underrepresented Populations

We do not expect the inclusion and exclusion criteria to either over or under-represent women, minorities, or underrepresented populations.

4. REGISTRATION PROCEDURES

4.1 General Guidelines for DF/HCC and DF/PCC Institutions

Patient Entry

Patients must be registered with the DF/HCC Quality Assurance Office for Clinical Trials (QACT)

([REDACTED]) prior to the start of treatment. Any patient not registered to the protocol prior to the start of treatment will be ineligible. The following information will be provided to the QACT:

- Registering physician (PI or coI) name, telephone number, and pager number
- Protocol name and number, and Date treatment begins
- Patient name, Date of birth, Patient ID number, Primary physician, Primary treatment institution, Confirmation of eligibility
- Copy of signed consent form.
- Patient must start treatment within 1 month of registration

CONFIDENTIAL

This document is confidential. Do not disclose or use except as authorized.

DF/HCC institutions will register eligible participants with the QACT central registration system. Registration must occur prior to the initiation of therapy. Any participant not registered to the protocol before treatment begins will be considered ineligible and registration will be denied.

A member of the study team will confirm eligibility criteria and complete the protocol-specific eligibility checklist.

Following registration, participants may begin protocol treatment. Issues that would cause treatment delays should be discussed with the Principal Investigator. If a participant does not receive protocol therapy following registration, the participant's protocol status must be changed. Notify the QACT Registrar of participant status changes as soon as possible.

4.2 Registration Process for DF/HCC and DF/PCC Institutions

The QACT registration staff is accessible on Monday through Friday, from 8:00 AM to 5:00 PM Eastern Standard Time. In emergency situations when a participant must be registered during off-hours or holidays, call the QACT registration line at [REDACTED] and follow the instructions for registering participants after hours.

The registration procedures are as follows:

1. Obtain written informed consent from the participant prior to the performance of any study related procedures or assessments.
2. Complete the protocol-specific eligibility checklist using the eligibility assessment documented in the participant's medical/research record. **To be eligible for registration to the study, the participant must meet each inclusion and exclusion criteria listed on the eligibility checklist.**
3. Fax the eligibility checklist(s) and all pages of the consent form(s) to the QACT at [REDACTED]
[REDACTED]
4. The QACT Registrar will (a) validate eligibility, (b) register the participant on the study, and (c) randomize the participant when applicable.
5. The QACT Registrar will send an email confirmation of the registration and/or randomization to the person initiating the registration immediately following the registration and/or randomization.

CONFIDENTIAL

This document is confidential. Do not disclose or use except as authorized.

4.3 General Guidelines for Other Participating Institutions

Please see section 5.7 of the Data Safety Monitoring Plan.

4.4 Registration Process for Other Participating Institutions

Please see section 5.7 of the Data Safety Monitoring Plan.

5. TREATMENT PLAN

5.1 Treatment Program

5.1.1 Assessments During Treatment

- Vital Signs: Pulse, Blood Pressure, Temperature obtained weekly
- Lab tests: CBC with diff (WBC, HGB, PLT, ANC, ALC), Liver and renal function tests (SGOT, SGPT, Total Bilirubin, Alkaline Phosphatase, Creatinine, BUN and Creatinine Clearance calculated with Cockcroft and Gault formula), LDH and Tumor markers (CEA, CA 19-9, alpha fetal protein) will be obtained weekly during treatment on study days 1, 8, 15 and the day of the last radiation treatment.

Patients will be seen at least once per week by a physician and a radiation oncology nurse while undergoing radiation treatment and will be assessed for acute toxicity.

5.1.2 Radiation Therapy

5.1.2.1 Pre-planning and Simulation Procedures

Prior to radiation planning, patients will undergo placement of fiducial seeds according to institutional procedures. If placement of fiducials is contraindicated in a patient, or if a patient is deemed too high risk for implanting procedure, the patient may proceed with study participation without fiducials at the discretion of the treating investigator.

5.1.2.2 Treatment Planning

Patients will undergo an abdominal 4D CT scan in the treatment position. Treatment planning will be done on a 4D CT-based planning system. If the motion of the GTV is less than or equal to 10mm, an ITV will be defined. If the motion is greater than 10mm, gating or deep inspiration breath hold (DIBH) will be used. For proton treatments, the patient will be in a customized immobilization device in the appropriate position. The treatment planning CT is to be performed with the patient in this device. The radiation oncologist will define the target and the non-target tissues/structures of interest on each section and specify the radiation dose constraints for each of the sensitive structures (uninvolved liver, kidney, large and small bowel, stomach, spinal cord). The treatment

CONFIDENTIAL

This document is confidential. Do not disclose or use except as authorized.

volume is defined as the tumor, visualized on the CT and/or MRI. Clinical Target Volume (CTV) expansion will be 0.5-1 cm at treating physician's discretion. The PTV shall be defined relative to the CTV on the basis of lateral uncertainties alone in the range of 0.5 to 1.0 cm. (Adjustments shall be made within the beam-design algorithm to take into account differences, if any, between the margins needed to account for uncertainties along the beam direction (range uncertainties) and those included in the lateral uncertainty defined PTV.)

5.1.2.3 Dose Fractionation and Specification

Proton treatments will be delivered at the Francis H. Burr Proton Therapy Center at the Massachusetts General Hospital using a 240 MeV cyclotron. At MDACC, proton treatments will be delivered at the MDACC Proton Therapy Center using a 250 MeV synchrotron. At the Roberts Proton Facility at the University of Pennsylvania, proton treatments will be delivered using a 230 MeV cyclotron. All treatments will be administered as one daily fraction, 5 days per week over 3 weeks. The RBE for proton irradiation is set at 1.1. Thus, the dose unit, Gy (RBE), is proton dose in Gy X RBE of 1.1. Based on the analysis of the results of the University of Michigan liver protocol there were no cases of liver toxicity for the average liver dose less than 30 Gy delivered in 1.5 Gy per fraction. In our protocol we intend to use **15 fractions, 5 daily fractions per week**.

For peripheral tumors the total dose will be as follows:

67.5 Gy (RBE) (NTD 81 Gy₁₀, 101 Gy₃) in 15 fractions

For central tumors (within 2 cm of porta hepatis), fractionation will be as follows:

58 Gy (RBE) (NTD 67 Gy₁₀, 79.6 Gy₃)

Underdosing of the PTV will be permitted to maintain normal tissue constraints as described below. However 90% of the PTV should receive the prescription dose. Dose de-escalation will be permitted to maintain a liver EUD below 20 Gy (RBE) and a mean liver dose ≤ 24 Gy (RBE). If dose is de-escalated to below 45 Gy (RBE), the patient will be removed from study and referred as appropriate for further management.

Normal Tissue Constraints:

Spinal cord max dose: 30 Gy (RBE)

Stomach max dose: 42 Gy (RBE)

Bowel (including duodenum, small bowel, large bowel) max dose: 45 Gy (RBE)

CONFIDENTIAL

This document is confidential. Do not disclose or use except as authorized.

Kidney V14 (volume receiving 14 Gy (RBE) < 30%)

Liver-GTV: EUD \leq 20 Gy (RBE), mean dose \leq 24 Gy (RBE)- whichever is lower.

Heart Max dose: 45 Gy (RBE), V40<10%

Chest Wall: no more than 2ccs may receive >60 Gy (RBE)

The deviations in dose constraints described above are considered planning deviations only and will not constitute protocol deviations. Treatment plans that include minor planning deviations may be delivered as part of this protocol. Treatment plans that include major planning deviations may be delivered on this protocol with the review and approval of the PI prior to treatment start. All relevant DVH data regarding doses to critical structures will be maintained in the study database for analysis.

Treatment will be administered on an outpatient basis. Expected toxicities and potential risks as well as dose modifications for are described in Section 6 (Expected Toxicities and Dosing Delays/Dose Modifications). No investigational or commercial agents or therapies other than those described below may be administered with the intent to treat the participant's malignancy.

5.2 Pre-treatment Criteria

Baseline staging requirements:

All assessments must be completed within 6 weeks of study entry, unless otherwise noted.

5.2.1 Complete history and physical examination by radiation oncologist and responsible medical oncologist or surgeon.

5.2.2 Laboratory evaluation: CBC with diff (WBC, HGB, PLT, ANC, ALC), Liver and renal function tests (SGOT, SGPT, Total Bilirubin, Alkaline Phosphatase, Creatinine, BUN and Creatinine Clearance calculated with Cockcroft and Gault formula), LDH and Tumor markers (CEA, CA 19-9, alpha fetal protein) sodium, potassium, chloride, carbon dioxide, calcium, phosphorous, PT/INR, Albumin, Child-Pugh classification, and tumor markers (CEA, CA 19-9, alpha fetal protein). Lab tests must be completed within 2 weeks of study entry.

5.2.3 Thoracic CT scan to exclude lung and mediastinal metastases.

5.2.4 Abdominal and Pelvic CT scan to exclude non-hepatic disease or metastases. **5.2.5** Hepatic MRI is required if any lesion is difficult to visualize and/or measure on the Abdominal/Pelvic CT scan.

5.3 Proton Beam Delivery

All charged particle treatment will be given with the patient at the Francis H. Burr Proton [name] Anderson Proton Therapy Center, or the University of Pennsylvania Roberts Proton Facility. Film or digital images will be taken prior to each treatment in accordance with the proton center's standard practice

CONFIDENTIAL

This document is confidential. Do not disclose or use except as authorized.

for all patients. These images are used to verify the position of the patient and the aperture. These images are permanently stored electronically for each patient. Respiratory gating or deep inspiration breath hold (DIBH) is recommended to account for respiratory excursion if tumor motion is > 10mm. Treatment may start any day of the week except Friday.

5.4 General Concomitant Medication and Supportive Care Guidelines

There are no required concomitant medications in this study. No other cytotoxic therapy or radiotherapy may be used during study treatment. Patients may receive all concomitant therapy deemed necessary to provide optimal support.

5.5 Duration of Therapy

Proton radiation therapy will in most instances be completed within 3 weeks of the start of treatment (15 consecutive hospital business days). This may be extended if patients require a break from treatment. Criteria for break would include any G3 or G4 toxicity. All labs will be assessed by the treating physician to determine whether they are considered clinically significant or not clinically significant and treatment will be held at their discretion. All patients experiencing any of the following events will be taken off treatment:

- Disease progression,
- Intercurrent illness that prevents further administration of treatment,
- Unacceptable adverse event(s),
- Participant decides to withdraw from the study, or
- General or specific changes in the participant's condition render the participant unacceptable for further treatment in the opinion of the treating investigator.

5.6 Duration of Follow Up

Study participants will be followed for five years from the completion of study treatment or until death, whichever occurs first. Participants will be removed from follow-up when any of the criteria listed in Section 5.5 apply. Participants removed from treatment or follow-up will be followed for survival outcomes and a 2 years analysis of local control.

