5.7 Criteria for Removal from Study

Participants will be removed from study upon death or withdrawal of consent. The reason for study removal and the date the participant was removed must be documented in the medical record and recorded in the study-specific case report form (CRF). Alternative care options will be discussed with the participant, if applicable.

CONFIDENTIAL

This document is confidential. Do not disclose or use except as authorized.

In the event of unusual or life-threatening complications, participating investigators must immediately notify the Principal Investigator [name] at [REDACTED]

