9.2 Data Collection

Weekly on-study labs are to be drawn on study days 1, 8, 15 and the day of the last radiation treatment. All patients will be evaluated initially, and at 1, 3, 6, 9, 12, 15, 18, 21, 24, 30, 36, 42, 48, 54, and 60 months post treatment. Each follow-up examination will consist of interval history and physical examination, toxicity assessment, liver function tests, LDH, PT INR, albumin, Child-Pugh classification and tumor markers (CEA, CA 19-9, alpha feta protein). Baseline and follow up physical examination will include clinical assessment of encephalopathy and ascites for calculation of Child-Pugh Score. Assessment of the liver tumor by CT and/ or MRI will be performed at time of abdominal imaging twice yearly for two years and then yearly for three years. Chest CT will be obtained twice yearly for two years and then yearly for three years. Additional imaging studies may be obtained for clinical follow up at the discretion of the treating clinicians. For study participants who receive follow up care at institutions other than the treating institution, imaging reports and scans must be sent to the treating institution to be included in the study data set.

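### Section 5.6 ends follow-up on the off-treatment criteria of 5.5, including progression, against the five-year schedule in 9.2; late-toxicity visits and local control after year 2 are exposed, the 2-year primary endpoint is not

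*Combined protocol and SAP*

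**What the plan says.** Section 5.6 has three sentences on follow-up. The first sets the rule: "Study participants will be followed for five years from the completion of study treatment or until death, whichever occurs first". The second removes people from it: "Participants will be removed from follow-up when any of the criteria listed in Section 5.5 apply". The third says what is kept: "Participants removed from treatment or follow-up will be followed for survival outcomes and a 2 years analysis of local control".

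The 5.5 list is introduced as a list of reasons to stop radiation: "All patients experiencing any of the following events will be taken off treatment". It names disease progression (not defined there), intercurrent illness that prevents treatment, unacceptable adverse events, the participant's decision to withdraw, and changes that make further treatment unacceptable.

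The other relevant passages are:
- Section 9.2 sets the visits: "All patients will be evaluated initially, and at 1, 3, 6, 9, 12, 15, 18, 21, 24, 30, 36, 42, 48, 54, and 60" months after treatment. On content it says "Each follow-up examination will consist of interval history and physical examination, toxicity assessment, liver function tests", among other items. Liver imaging is "twice yearly for two years and then yearly for three years".
- Section 14.2 states follow-up of at least five years or until death, citing 5.6.
- Section 5.7 says "Participants will be removed from study upon death or withdrawal of consent".
- Objective 1.3.1 is safety and tolerance. Objective 1.3.3 includes 5-year local control in hepatocellular cancer. Section 14.4 lists late toxicity as a secondary endpoint, reported as rates with exact binomial intervals.

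**The concern.** A list written to stop treatment is reused to stop follow-up. Progression is the item that matters most after treatment ends. The only definition of progressive disease, in 10.2, includes any new lesion. Local failure in 10.3 is confined to the treated lesions, and a new lesion elsewhere in the liver is classed separately. A patient whose treated tumor is controlled but who develops a lesion elsewhere would therefore leave follow-up, although that patient is still informative for local control and still at risk of late radiation effects. Section 2.3 itself points to out-of-field progression in this disease.

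Two secondary results are at stake:
- **Late toxicity.** Section 6.1 defines late effects as those more than 3 months after radiation. No passage schedules a toxicity assessment for removed patients. Section 14.4 states no denominator rule, so late-toxicity rates may be understated if patients who are no longer examined stay in the denominator.
- **Five-year local control in hepatocellular cancer (1.3.3).** The third sentence of 5.6 keeps local control only for the 2-year analysis.

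Sites that follow 9.2 lose nothing, but sites reading the same protocol could follow different rules.

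**Working it through.** **1. Primary design figures.** Section 14.1 gives n = 30 alive at 2 years (60 × 0.50), success at 21 or more, and rates of 55% versus 80%. The exact binomial gives P(X ≥ 21 | 30, 0.80) = 0.939 and P(X ≥ 21 | 30, 0.55) = 0.069, matching the stated 94% and 7%. The third sentence of 5.6 keeps 2-year local control for removed patients, so none of these figures changes.

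**2. Passages side by side.**

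| Place | Who | Until when |
|---|---|---|
| 5.6, first sentence | participants | five years or death |
| 5.6, second sentence | anyone meeting a 5.5 criterion | removed from follow-up |
| 5.6, third sentence | those removed from treatment or follow-up | survival and 2-year local control |
| 9.2 | all patients | month 60, toxicity at each visit |
| 14.2 | the patients | at least five years or death, citing 5.6 |
| 5.7 | participants | removed from study only on death or withdrawal of consent |

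The second row cannot be met together with the fourth. Section 14.2 agrees with 9.2 but only imports 5.6, so it is a weaker witness. Section 5.7 speaks of removal from study rather than from follow-up, so it sits badly with the second sentence without strictly contradicting it.

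**3. One patient.** Section 9.2 lists 15 follow-up visits. Removal just after the month 6, 12 or 24 visit forfeits 12, 10 or 6 of them. After year 2 it also forfeits the three yearly liver scans.

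**4. Sixty hepatocellular patients (illustration).** The documents give no progression rate. Assumed: a proportion q = 0.30 to 0.60 progresses elsewhere by month 24. Survival scenarios:
- A: 50% at 2 years (14.1) with a constant hazard, so 0.5^2.5 = 17.7% at 5 years.
- B: 50% at 2 years and 23% at 5 years (2.3).
- C: 70% at 2 years (top of the range in 14.1) and 23% at 5 years.

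Visits due at month t = 60 × S(t). If progression is independent of death, visits lost = 60 × S(t) × F(t). With a constant hazard, F(t) = 1 − (1 − q)^(t/24). If progression stops at year 2, F(t) = q after month 24.

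Example, scenario A, q = 0.30, month 30: S = 0.5^1.25 = 0.420, so 25.2 are due. F = 1 − 0.7^1.25 = 0.360, so 9.1 are lost. Over months 30, 36, 42, 48, 54 and 60 the losses are 9.1 + 8.8 + 8.3 + 7.6 + 7.0 + 6.3, or 47.

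If progressors die sooner, the two times can be joined by a Clayton copula with θ = 2τ/(1 − τ). Then visits lost = 60 × {S − [S^(−θ) + (1 − F)^(−θ) − 1]^(−1/θ)}. For scenario A, q = 0.30, τ = 0.5 (θ = 2), month 30, this is 60 × (0.420 − 0.375) = 2.7 rather than 9.1.

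Visits after month 24, at q = 0.30 / 0.60:

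| | Due | Constant hazard, independent | Stops at year 2, independent | Constant hazard, τ = 0.3 | Constant hazard, τ = 0.5 |
|---|---|---|---|---|---|
| A | 102.5 | 47 / 80 | 30.7 / 61.5 | 23 / 57 | 10 / 44 |
| C | 138.4 | 63 / 108 | 41.5 / 83.0 | 38 / 86 | 21 / 75 |

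Scenario B falls between A and C throughout. A constant hazard is a strong assumption: 30-60% by year 2 implies 1 − 0.7^2.5 = 59% to 1 − 0.4^2.5 = 90% progressed by year 5.

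**5. Five-year survivors still in full follow-up (independent case).** Expected survivors are 60 × 0.177 = 10.6 to 60 × 0.23 = 13.8. Under a constant hazard, 10.6 × 0.4^2.5 = 1.1 to 13.8 × 0.7^2.5 = 5.7 remain. If progression stops at year 2, 10.6 × 0.4 = 4.2 to 13.8 × 0.7 = 9.7 remain.

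**6. Months 6 to 24.** The constant-hazard independent calculation gives 51-138 of 276-337 toxicity visits lost. This is an upper limit, because imaging contacts for the 2-year analysis continue and toxicity may be recorded at them.

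**The case against.** The strongest defense reads 5.6 as default, exception and remainder: five years for most, removal for some, and a deliberate reduced follow-up for those removed. The third sentence shows that the authors foresaw removal. As a reading of 5.6 alone this is coherent. It fails against 9.2, which puts all patients on the schedule to month 60 without exception.

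Several limits on the concern stand:
- Two of the five 5.5 items are worded around giving treatment and cannot sensibly arise after it ends. Withdrawal by the participant is a proper reason to stop. That leaves progression and the patients who stop for adverse events; the figures above model progression only.
- Some data would still arrive. Section 6.1 collects related Grade 2 or higher toxicity until the final study visit, and 11.1 follows ongoing events. Sections 9.1 and 9.2 allow clinical imaging and require outside scans to be sent in. None of these schedules an examination for new late effects in a removed patient.
- The rates, the independence assumption and the copula parameters are assumptions.

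A reader might infer three stronger things that the documents do not support. One is that the primary analysis is compromised; the third sentence of 5.6 keeps it. Another is that removed patients would definitely be counted as free of toxicity; 14.4 gives no rule either way. The third is that the cholangiocarcinoma objective 1.3.4 also needs local control after year 2; there the five-year time point attaches to survival, and local control has none.

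**Conclusion.** The concern holds for secondary endpoints. The second sentence of 5.6 conflicts with the first sentence and with 9.2, and the protocol does not say which governs. If it is followed, scheduled detection of new late toxicity (1.3.1, 14.4) and 5-year local control in hepatocellular cancer (1.3.3) lose data from patients who progress outside the treated lesions.

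The size is illustrative. With 30-60% progressing by 2 years, independently of death, 47-108 of about 103-138 visits due after month 24 are lost under a constant hazard, and 31-83 if progression stops at year 2. If progressors die sooner (τ 0.3-0.5, constant hazard), 10-86 are lost. If sites already follow 9.2, the loss is nil. Survival, 2-year local control and the 94% and 7% in 14.1 are unaffected. The text should be corrected, with medium confidence in how much it matters in practice.

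**What to change.** Reconcile 5.6 with 9.2 and 14.2:
- Delete the second sentence of 5.6 and state that the 5.5 criteria end treatment only.
- Amend the third sentence as well, because it would still limit patients taken off treatment to survival and 2-year local control. State that patients taken off treatment or progressing stay on the Section 9 toxicity visits and scheduled liver imaging to 60 months, death or withdrawal of consent.
- In 14.1, state that meeting a 5.5 criterion other than withdrawal does not count as dropping out and does not by itself censor local control.
- Reconcile the removal from study in 6.4 with 5.7.

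No comment is made on the treatment-stopping criteria themselves.

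The cost is protocol wording plus visits already in Section 9. Scans restored at months 36, 48 and 60 under 9.2 number about 23-51 of 47-63 due in the constant-hazard independent case. They number 14-38 if progression stops at year 2 (47 × 0.30 to 63 × 0.60), and 4-40 if progressors die sooner. The count would be higher under the 9.1 calendar, which shows twice-yearly imaging with no later step to yearly. Late events arising after subsequent therapy will also be harder to attribute to protons.
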